Contact IRT	X	X	X	X	X	X	X	X	X	X	X			Section 8.1.3
Dispense eDiary (handheld device) and instruct participant on use	X													Section 8.2.1.3
Randomization		X												Section 6.4
Dispense study drug		X	X	X	X	X	X	X	X	X				Section 6.1
Administer study drug at site		X	X	X	X	X	X	X	X	X	X			
Administer background therapy at site		X	X	X	X	X	X	X	X	X	X			
Distribute reminder card	X	X	X	X	X	X	X	X	X	X	X			Section 8.1.4
Distribute participation card	X													Section 8.1.5

Table 3: Schedule of Activities (Continued)

Visit Day (Range)	Screening	PC Period (12 Weeks)				EXT Period (24 Weeks)						Post-Treatment Follow-Up	Notes and Protocol Section
	Days -28 to -1	Baseline Day 1	Week 4 (± 3 d)	Week 8 (± 3 d)	Week 12/ EOT1 (or ET1) (± 3 d)	Week 16 (± 3 d)	Week 20 (± 3 d)	Week 24 (± 3 d)	Week 28 (± 3 d)	Week 32 (± 3 d)	Week 36/ EOT2 (or ET2) (± 3 d)	Week 44/ EOS (± 7 d)	
Administrative procedures (continued)													
Collect study drug and review drug compliance			X	X	X	X	X	X	X	X	X		Section 6.5
Follow-up phone call for eDiary compliance	X*		X†		X*								Section 8.2.1.2.1 * 1 week before visit. † 2 weeks before visit.
Review eDiary compliance		X	X	X	X	X	X	X	X	X	X		Section 8.2.1.2.2
Safety assessments													
AE assessments	X	X	X	X	X	X	X	X	X	X	X	X	Section 8.3.1
Contraception check	X	X	X	X	X	X	X	X	X	X	X	X	Section 5.3.1
Comprehensive physical examination	X				X						X		Section 8.3.2
Targeted physical examination		X	X	X		X	X	X	X	X		X	
Weight/height	X	X			X			X			X	X	Section 8.3.2 Height at screening only.
Vital signs	X	X	X	X	X	X	X	X	X	X	X	X	Section 8.3.3
12-lead ECG	X				X						X		Section 8.3.4

Table 3: Schedule of Activities (Continued)

Visit Day (Range)	Screening	PC Period (12 Weeks)				EXT Period (24 Weeks)						Post-Treatment Follow-Up	Notes and Protocol Section
	Days -28 to -1	Baseline Day 1	Week 4 (± 3 d)	Week 8 (± 3 d)	Week 12/ EOT1 (or ET1) (± 3 d)	Week 16 (± 3 d)	Week 20 (± 3 d)	Week 24 (± 3 d)	Week 28 (± 3 d)	Week 32 (± 3 d)	Week 36/ EOT2 (or ET2) (± 3 d)	Week 44/ EOS (± 7 d)	
Efficacy assessments													
PROs													
eDiary (UAS/AAS)	Daily from screening through Week 44 (or ET, if applicable)											Sections 8.2.1.3, 8.2.1.4, and 8.2.1.5 Handheld device.	
Quality of life assessments													
Laboratory assessments													
Serum FSH (WONCBP only)	X												Section 8.3.5

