6.5.2. Compliance With Background Therapy

Participants will be instructed to record background therapy administration in the eDiary from the screening visit until completion of the post-treatment follow-up visit (EOS). Compliance with background therapy will also be documented in the participant's study source documentation and monitored by the investigator (or designee).

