6.7.4. Prohibited Medications and Procedures

The following medications and procedures are prohibited for all participants in the study:

- Conventional therapies with potential therapeutic impact on CSU, per discretion of the investigator or designee, with the exception of SOC and rescue medication.
- JAK inhibitors (systemic or topical) other than povorcitinib.
- Use of biologics with immunomodulatory effect.
- Systemic immunosuppressive or immunomodulating drugs (eg, oral or injectable corticosteroids, methotrexate, cyclosporine, dapsone, azathioprine).
- Apremilast, crisaborole, or any other systemic or topical PDE-4 inhibitor.

- Strong systemic CYP3A4 inhibitors and strong and moderate systemic CYP3A4 inducers (see [Appendix B](#)). Examples include but are not limited to the following medications: rifampicin/rifampin, ketoconazole, itraconazole, carbamazepine, ritonavir, St John's wort, and grapefruit/grapefruit juice.
 - In exceptional cases (eg, COVID-19 treatment with nirmatrelvir/ritonavir), and after study drug interruption, strong CYP3A4 inhibitors or strong/moderate inducers may be used for up to 7 days. The sponsor (or designee) must be informed of the investigator's (or designee's) decision and rationale within a reasonable timeframe. Study drug may be restarted after a minimum of 7 days of discontinuation of the strong CYP3A4 inhibitor or strong/moderate inducer.
 - If treatment with strong CYP3A4 inhibitors or strong/moderate CYP3A4 inducers is required for longer than 7 days after study drug interruption, the participant may be discontinued from the study and the ET visit performed.
- Live, attenuated vaccines (during the study and within 8 weeks after the last dose of study drug). Examples of live vaccines include but are not limited to the following:
 - BCG
 - herpes zoster
 - measles-mumps-rubella or measles-mumps-rubella-varicella
 - monovalent, live, attenuated influenza A (intranasal)
 - oral polio vaccine
 - rotavirus
 - seasonal, trivalent, live, attenuated influenza (intranasal)
 - smallpox
 - typhoid
 - varicella (chickenpox)
 - yellow fever
- Elective surgery
 - PC period: Will not be allowed
 - EXT period: May be allowed per determination of the investigator (or designee) after consultation with the sponsor (or designee). See Section [6.6.1.6](#) for details on study drug interruption.

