7. DISCONTINUATION OF STUDY TREATMENT AND PARTICIPANT WITHDRAWAL

7.1. Discontinuation of Study Treatment

7.1.1. Reasons for Discontinuation

Participants **must** be discontinued from study treatment for the following reasons:

- The participant becomes pregnant.
- Consent is withdrawn.

Note: Consent withdrawn means that the participant has explicitly indicated that they do not want to be followed any longer; in this case no further data, except data in the public domain, may be solicited from or collected on the participant. Consent may also be partial. Participants may choose to discontinue study drug and remain in the study to complete the post-treatment follow-up visit.

- Further participation would be injurious to the participant's health or well-being, in the investigator's medical judgment.
- Occurrence of unacceptable toxicity as noted in Section 6.6.
- Has received a prohibited medication or procedure as described in Section 6.7.4.
- The study is terminated by the sponsor.
- The study is terminated by the local health authority, IRB, or IEC.

A participant **may** be discontinued from study treatment as follows:

- If a participant is consistently noncompliant with study procedures or with study drug or background therapy administration in the investigator's opinion, the sponsor should be consulted for instruction on handling the participant.

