8.7. End of Treatment and Early Termination

The EOT1 (PC period) coincides with the Week 12 visit, and the EOT2 (EXT period) coincides with the Week 36 visit. A participant who completes the Week 12/EOT1 visit will have completed the PC period and may continue into the EXT period. A participant who completes the Week 36/EOT2 visit will have completed the EXT period.

If a decision is made that the participant will permanently discontinue study drug prior to the Week 36/EOT2 visit, then the ET visit should be conducted and will be determined as ET1 (if during the PC period) or ET2 (if during the EXT period). If the ET visit coincides with a regular study visit, then the ET evaluations will supersede those of that scheduled visit, and the data should be entered in the ET visit in the eCRF. If this decision does not coincide with a regular visit, reasonable efforts should be made to have the participant return to the site to complete the ET procedures. The participant should be encouraged to return for the follow-up visit.

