10.4.1. Primary Analysis

The primary estimand and the strategies for addressing the defined intercurrent events are provided in [Table 15](#) and [Table 16](#), respectively.

Table 15: Estimand for Primary Endpoint

Primary Endpoint	Population	Treatment	Population-Level Summary
Change from baseline in the weekly UAS7 at Week 12.	Participants aged 18 to 65 years who have had a diagnosis of CSU for ≥ 3 months that is inadequately controlled by second-generation H1 antihistamines.	Each of the povorcitinib dose groups compared with placebo	The estimated mean change from baseline in UAS7 for each treatment group, as well as the difference in the estimated mean change from baseline in UAS7 score in each active treatment group as compared with the placebo group, at Week 12.

Table 16: Intercurrent Events and Strategies for the Primary Estimand

Intercurrent Event	Strategies for Addressing the Intercurrent Event
Treatment discontinuation due to any reason	The data collected for the variable are used regardless of whether or not the participant discontinues treatment due to any reason (treatment policy strategy)
Initiation of Protocol-allowed rescue medication	The data collected for the variable are used regardless of whether or not the participant starts the use of any Protocol-allowed rescue medication (treatment policy strategy)

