**Table 5: Intercurrent Events and Strategies for the Primary Estimand**

Intercurrent Event	Strategies for Addressing the Intercurrent Event
Treatment discontinuation due to any reason	The data collected for the variable are used regardless of whether the participant discontinues treatment due to any reason (treatment policy strategy)
Initiation of Protocol-allowed rescue medication	The data collected for the variable are used regardless of whether the participant starts the use of any Protocol-allowed rescue medication (treatment policy strategy)

The primary analysis will be performed in the FAS. The mean change from baseline at Week 12 in weekly UAS7 score will be assessed using an MMRM to include all available data at postbaseline visits during the PC period up to Week 12. Participants who have a baseline value and at least 1 postbaseline value during the PC period will be included in the analysis. The MMRM will include change from baseline up to Week 12 as a response variable and the fixed effect of treatment group, randomization stratification factor (previous use of an anti-IgE biologic [yes or no]), visit, treatment-by-visit interaction, and covariates of baseline value and

baseline value by visit interaction. Unstructured covariance matrix will be assumed for the within-participant errors.

Compound symmetry covariance matrix will be used if the model with unstructured variance covariance does not converge. The Kenward-Roger method will be used to estimate the degrees of freedom. Missing data will not be imputed. The least squares mean estimates for each treatment group and the associated covariance matrix obtained from the MMRM will be provided and further used in the generalized MCP-mod framework.

At the MCP stage, contrast test statistics and multiplicity adjusted p-value for the contrast test will be provided for each prespecified candidate model. A dose-response relationship will be declared if at least 1 model among the set of 6 prespecified candidate models is identified to be statistically significant at the level  $\alpha = 0.025$  1-sided trend test. Once a significant dose-response is established, the best model will be selected using Akaike Information Criterion.

At the mod stage, the selected model will be used to obtain the dose-response curve and the 95% CI. The estimated dose-response curve will be presented graphically.

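### The primary estimand follows participants after they stop study drug, but the plan does not clearly secure or use their Week 12 UAS7

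*SAP*

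**What the plan says.** **Estimand.** Protocol 10.4.1 (Table 16) and SAP 7.3 (Table 5) agree. The SAP wording is "The data collected for the variable are used regardless of whether the participant discontinues treatment due to any reason (treatment policy strategy"; the protocol wording is "The data collected for the variable are used regardless of whether or not the participant discontinues treatment due to any reason (treatment policy strategy".

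**Diary.** The UAS row of the Schedule of Activities (Protocol Table 3) reads "Daily from screening through Week 44 (or ET, if applicable". Inclusion criterion 6 (Protocol 5.1) and Protocol 8.2.1.3 describe daily completion throughout the study. Protocol 6.5.2 has participants "record background therapy administration in the eDiary from the screening visit until completion of the post-treatment follow-up visit (EOS".

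**Visits after stopping drug.** Protocol 8.7 covers a decision to "permanently discontinue study drug prior to the Week 36/EOT2 visit, then the ET visit should be conducted"; in the placebo-controlled period this is ET1. Protocol 6.7.4 attaches the same visit to leaving the study: "the participant may be discontinued from the study and the ET visit performed". Protocol 7.1.1 says "Participants may choose to discontinue study drug and remain in the study to complete the post-treatment follow-up visit", and 7.1.2 allows efficacy assessments to continue in follow-up. Under Protocol 8.8.1, follow-up falls 60 (±7) days after the last dose when there is no Week 36 visit.

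**Derivation and analysis.** SAP 7.2.1.1 computes by-visit UAS7 from the seven days before the visit day and sets it to missing if more than two days are absent. A version anchored on any diary day is given for time-to-event endpoints only. SAP 7.3 fits an MMRM to available data without imputation.

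**The concern.** A treatment-policy estimand asks what happened at Week 12 to everyone randomized and treated, including those who stopped. If a stopper's Week 12 diary is not collected, or is collected and not turned into a UAS7, the MMRM predicts the value from earlier visits, mostly on drug, and from participants who stayed on drug. The estimate then drifts from the stated question toward what would have happened had they continued. What is at stake is the estimated benefit over placebo and the fitted dose-response curve, which are the main products of a dose-ranging trial.

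**Working it through.** **1. Diary collection.** The parenthetical in Table 3 has two readings.

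| Reading of ET | Support | Consequence |
|---|---|---|
| Stopping study drug | Protocol 8.7 | Diary ends at ET1; no Week 12 entries if ET1 is earlier |
| Leaving the study | Protocol 6.7.4; fits 5.1, 6.5.2, 7.1.2 and 8.2.1.3 | Diary continues while the participant stays in the study |

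**2. Timing under the second reading.** Taking Week 12 as nominal Day 12 × 7 + 1 = 85 (an assumption, using the day numbering in SAP 4.1.2), follow-up at last dose + 60 days falls before Day 85 if the last dose is before Day 85 − 60 = 25. With the ±7-day window the cut-off lies between Day 85 − 67 = 18 and Day 85 − 53 = 32. Such a participant can complete the last visit before Week 12.

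**3. Derivation.** After ET1 no passage schedules a Week 12 visit for someone off drug. By-visit UAS7 needs a visit day, so Week 12 diary entries that exist could go unused. No visible rule places an off-schedule ET1 value in the MMRM.

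**4. Analysis.** SAP 7.3 is followed only by subgroup summaries (7.3.1). The contents list and the visible part of Appendix A show no sensitivity analysis of the mean change.

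**5. Size.** Planning inputs (Protocol 10.1): mean changes of −8 and −17, difference 9, SD 13, 34 per group. A simulated MCP-mod calculation from these gives a minimum power of 0.849 against the stated 0.85, so the planning figures reproduce. The planning standard error of a pairwise difference is 13 × √(2/34) = 3.15.

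Assumed inputs, none given in the documents:
- p, the share of the 75 mg group stopping before Week 12: 5% to 20% (1.7 to 6.8 of 34).
- m, the share of stoppers with no Week 12 value: one half or all.
- f, the share of the 9-point effect that stoppers lose: one half or all.

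The true treatment-policy effect is 9(1 − pf). The mean effect among those observed is 9[1 − p(1 − m)f/(1 − pm)]. The difference is

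overstatement = 9·p·f·m·(1 − p)/(1 − pm).

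| p | m = ½, f = ½ | m = ½, f = 1 | m = 1, f = ½ | m = 1, f = 1 |
|---|---|---|---|---|
| 0.05 | 0.11 | 0.22 | 0.23 | 0.45 |
| 0.10 | 0.21 | 0.43 | 0.45 | 0.90 |
| 0.20 | 0.40 | 0.80 | 0.90 | 1.80 |

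Middle case: 9 × 0.10 × 0.5 × 0.5 × 0.90/0.95 = 0.21 points; 0.21/3.15 = 0.07 SE. Extremes: 0.11/3.15 = 0.03 SE and 1.80/3.15 = 0.57 SE.

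A large-sample simulation of a two-visit MMRM (1,000,000 per arm, correlation 0.4 or 0.7, stopping more likely after a poor Week 4 score, assumed Week 4 means −5 and −11) agreed with the formula to about 0.01 point.

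**6. No drug effect.** There is then no effect to lose and the overstatement is zero. The simulation at p = 0.20, m = 1 gave an MMRM difference of −0.04 against a true sample difference of −0.03.

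**The case against.** **Is it a contradiction?** A reader might infer that the diary passages flatly conflict, or that post-discontinuation data will not be collected. The documents do not support either. There is one ambiguous parenthetical, and one of its readings agrees with every other diary passage. What stands is that a site could follow the other reading, and that Protocol 8.8.1 can end participation before Week 12 either way.

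**Is a Week 12 visit implied?** Protocol 10.4 and SAP Section 3 run the primary analysis once everyone has completed Week 12 or left the study, and SAP 6.2 counts stopping treatment separately from withdrawing. Together these imply that someone off drug but still in the study reaches Week 12. That is fair, but it is not scheduled: Protocol 8.7 and 8.8.1 name only ET and follow-up.

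**Does the ET visit overwrite UAS7?** Protocol 8.7 says "If the ET visit coincides with a regular study visit, then the ET evaluations will supersede those of that scheduled visit", and a reader might infer that this distorts the score. It does not: UAS7 comes from the same seven diary days whichever visit label is used. Only an off-schedule ET1 raises a question.

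**Unseen text.** Parts of SAP 7.1 and 7.2 are not shown, so a window or ET1 rule may exist. That would settle the derivation point but not the diary wording.

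**Mitigation.** The Week 12 responder endpoints use nonresponder imputation (SAP 7.4.1), so a stopper without a value counts as a failure. This is a useful conservative companion, though not a test of the mean change. An MMRM under MAR is also a common primary analysis, and Protocol 2.2.1 calls the study proof-of-concept.

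**Conclusion.** The point holds as a gap between the estimand and the procedures. The Week 12 UAS7 of participants who stop study drug is neither clearly secured nor clearly used, and nothing visible tests the MAR assumption that fills the gap.

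The size is modest in the middle case, about 0.2 points or 0.07 SE, and ranges from 0.11 to 1.80 points over the assumed inputs. The upper end needs 20% stopping, all of them without a Week 12 value and all of the effect lost. The overstatement is zero if all Week 12 diaries are kept and used, if nobody stops, or if no effect is lost. Its sign could change if stoppers start another effective treatment. Only 75 mg versus placebo was quantified.

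A reader might infer a risk of a false dose-response finding. The mechanism does not produce one: with no drug effect it creates no difference, so type I error of the trend test is not inflated. The matter is worth fixing, with medium confidence, because the remedy is cheap.

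**What to change.** 1. **Protocol.** Reconcile the Table 3 diary row with 8.2.1.3, 8.7 and 8.8.1. Participants who stop study drug but have not withdrawn consent for data collection should keep completing the eDiary through Week 12, even when the 60-day follow-up visit falls earlier.
2. **SAP 7.2.1.1.** When there is no Week 12 visit, derive Week 12 UAS7 from a fixed study-day window, for example Days 78–84 (the seven days before nominal Day 85) with at least 5 of 7 entries, using the day-anchored logic already there. State that an off-schedule ET1 value is assigned by study day and that a value from an earlier week is not used as Week 12.
3. **SAP 7.3.** Add one prespecified sensitivity analysis for Week 12 values missing after discontinuation (reference-based multiple imputation or a tipping-point analysis), and report the number of such values by group.

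The protocol is dated 07 MAR 2023 and the SAP 20 MAR 2025. If the placebo-controlled period is over, only items 2 and 3 apply, with a statement that the MMRM relies on MAR for these participants.

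The cost is a few more weeks of diary entries, on a device already issued, for those who stop (about 7 to 27 of 136 at the assumed 5% to 20%), some SAP wording and one extra analysis.

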10. STATISTICS

10.1. Sample Size Determination

Approximately 136 participants will be randomly assigned to 4 treatment groups (placebo or povorcitinib 15, 45, or 75 mg) in a 1:1:1:1 ratio.

The sample size is based on the primary efficacy endpoint, the change in weekly UAS7 score from baseline at Week 12. Based on a Phase 2b study (Maurer et al 2022), the mean change in UAS7 score at Week 12 is assumed to be -8 in the placebo group and -17 in the povorcitinib 75-mg group, with a common STD of 13. A sample size of 34 participants per group is sufficient to test for the presence of a dose-response relationship, based on the MCP-mod approach (Bretz et al 2005, Pinheiro et al 2013).

This sample size provides a minimum power of 0.85 to detect a dose effect at a 1-sided 2.5% significance level with the linear, log-linear, E_{max} , and quadratic models prespecified as candidates to characterize the underlying dose-response curve for povorcitinib on the mean change in weekly UAS7 score at Week 12. The set of candidate dose-response models and their corresponding dose-response curves are shown in Table 12 and Figure 2, respectively.

[figure not shown]
Table 12: Prespecified Candidate Models

Model	$f(d, \theta)^a$	$f^0(d, \theta)^b$	Initial Value(s) for Parameter(s)
Linear	$E_0 + \delta d$	d	Not applicable
Linear log-dose	$E_0 + \delta \log(d + 1)$	$\log(d + 1)$	Not applicable
E_{max1}	$E_0 + \frac{E_{max}d}{ED_{50} + d}$	$\frac{d}{ED_{50} + d}$	$ED_{50} = 20$
E_{max2}			$ED_{50} = 30$
Sigmoid- E_{max}	$E_0 + \frac{E_{max}d^h}{ED_{50}^h + d^h}$	$\frac{d^h}{ED_{50}^h + d^h}$	$ED_{50} = 30, h = 2$
Quadratic	$E_0 + \beta_1 d + \beta_2 d^2$	$d + \frac{\beta_2}{ \beta_1 } d^2$	$\delta = \frac{\beta_2}{ \beta_1 } = -0.0083$

^a d is dose ($d = 0$ for placebo group), θ refers to the vector of model parameters, E_0 is the placebo effect for all candidate models (0.1), E_{max} is the maximum treatment effect over placebo, ED_{50} is the dose that gives 50% of the maximum effect for E_{max} model.

^b Standardized model.

Figure 2: Prespecified Dose-Response Curves

For a reference of different assumptions of STD of the change in UAS7 score from baseline at Week 12, the sample sizes and the corresponding minimum power to detect a significant dose-response signal at a 1-sided 2.5% significance level are provided in [Table 13](#).

Table 13: Samples Sizes and Minimum Power Across the 6 Prespecified Candidate Models Under Different Assumptions of Standard Deviation

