10.3. Level of Significance

The dose response will be tested at a 1-sided 0.025 level. No multiplicity adjustment will be applied for other statistical tests. Two-sided 95% CIs will be reported for all analyses when appropriate.

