The primary analysis will be performed in the FAS. The mean change from baseline at Week 12 in weekly UAS7 score will be assessed using an MMRM to include all available data at postbaseline visits in the PC period up to Week 12. Participants who have a baseline value and at least 1 postbaseline value in the PC period will be included in the analysis. The MMRM will include change from baseline to Week 12 as a response variable, and the fixed effect of treatment group, randomization stratification factor (previous use of an anti-IgE biologic [yes or no]), visit, treatment-by-visit interaction, and covariates of baseline value and baseline value by visit interaction. Unstructured covariance matrix will be assumed for the within-participant errors. Compound symmetry covariance matrix will be used if the model with unstructured variance covariance does not converge. The Kenward-Roger method will be used to estimate the degrees of freedom. Missing data will not be imputed. The least squares mean estimates for each treatment group and the associated covariance matrix obtained from the MMRM will be provided and further used in generalized MCP-mod framework.

At the MCP stage, a contrast test statistics and multiplicity adjusted p-value for the contrast test will be provided for each prespecified candidate model. A dose-response relationship will be declared if at least 1 model among the set of 6 prespecified candidate models is identified to be

statistically significant at the level $\alpha = 0.025$ 1-sided trend test. Once a significant dose-response is established, the best model will be selected using Akaike Information Criterion.

At the Mod stage, the selected model will be used to obtain the dose-response curve and the 95% CI. The estimated dose-response curve will be presented graphically.

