**Table 2: Prespecified Candidate Models**

Model	$f(d, \theta)^a$	$f^0(d, \theta)^b$	Initial Value(s) for Parameter(s)
Linear	$E_0 + \delta d$	$d$	Not applicable
Linear log-dose	$E_0 + \delta \log(d + 1)$	$\log(d + 1)$	Not applicable
$E_{max1}$	$E_0 + \frac{E_{max}d}{ED_{50} + d}$	$\frac{d}{ED_{50} + d}$	$ED_{50} = 20$
$E_{max2}$			$ED_{50} = 30$
Sigmoid- $E_{max}$	$E_0 + \frac{E_{max}d^h}{ED_{50}^h + d^h}$	$\frac{d^h}{ED_{50}^h + d^h}$	$ED_{50} = 30, h = 2$
Quadratic	$E_0 + \beta_1 d + \beta_2 d^2$	$d + \frac{\beta_2}{ \beta_1 } d^2$	$\delta = \frac{\beta_2}{ \beta_1 } = -0.0083$

a  $d$  is dose ( $d = 0$  for placebo group),  $\theta$  refers to the vector of model parameters,  $E_0$  is the placebo effect for all candidate models (0.1),  $E_{max}$  is the maximum treatment effect over placebo, and  $ED_{50}$  is the dose that gives 50% of the maximum effect for the  $E_{max}$  model.

b Standardized model.

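### The dose-response curve's 95% CI ignores the AIC selection step, so it under-covers clearly at 15 mg and 30 mg, mildly to moderately at 45 mg, and hardly at all at 75 mg.

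*SAP*

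**What the plan says.** SAP 7.3 feeds the Week 12 LS means and their covariance matrix from the MMRM into generalized MCP-Mod. If any of the six contrasts is significant, "Once a significant dose-response is established, the best model will be selected using Akaike Information Criterion". The SAP continues: "At the mod stage, the selected model will be used to obtain the dose-response curve and the 95% CI". Protocol 10.4.1 has the same step: "At the Mod stage, the selected model will be used to obtain the dose-response curve and the 95% CI".

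SAP Table 2 ("Prespecified Candidate Models") lists linear, linear in log(d + 1), two Emax shapes (ED50 20 and 30), a sigmoid Emax and a quadratic. Neither document names a method for the curve's CI, mentions model averaging or a bootstrap over the selection, or labels the interval as conditional on the chosen model. An ordinary interval from the one selected model is therefore the plain reading, though it is not spelled out.

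SAP Table 4 defines the primary estimand as the mean change per group and each dose's difference from placebo. Those come from the MMRM and do not depend on the selected model.

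**The concern.** The same four dose means both choose the model and supply its interval. An interval computed as if the family had been known in advance leaves out the uncertainty about the family.

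That uncertainty is large here. Once parameters are fitted, the two Emax shapes are one family, so there are five distinct models: linear and log-linear with 2 parameters, Emax and quadratic with 3, and sigmoid Emax with 4 parameters for 4 dose levels. AIC charges 2 per parameter, so with 34 per arm it will usually return a two-parameter model whatever the true shape. Those models borrow heavily from the other arms at low doses, which is legitimate only if the family is right.

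At stake is how the lower end of the curve is read in a dose-ranging study. The 15 mg dose is where the question is most open: Protocol 2.2.2 sets it as the low end on hidradenitis suppurativa results that mostly did not separate statistically from placebo.

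**Working it through.** **Inputs.** Protocol 10.1: "the mean change in UAS7 score at Week 12 is assumed to be -8 in the placebo group and -17 in the povorcitinib 75-mg group", so a 9-point effect; "with a common STD of 13"; 34 per group; doses 0, 15, 45 and 75 mg. Protocol 10.3: "The dose response will be tested at a 1-sided 0.025 level". Shapes: SAP Table 2. Assumed, because the documents are silent: known variance, no dropout, ED50 bounded at 0.075-112.5 mg, h bounded at 0.5-10, delta-method CI.

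**1. The plan's own figure.** Protocol 10.1 states: "This sample size provides a minimum power of 0.85 to detect a dose effect at a 1-sided 2.5% significance level". With optimal contrasts for the six shapes and a maximum-contrast critical value of 2.19, simulated minimum power is 0.846 at 34 per group and SD 13, 0.855 at 25 and SD 11, and 0.847 at 29 and SD 12. The plan gives 0.85, 0.85 and 0.84, so it is reproduced.

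**2. Why the intervals are narrow at 15 mg.** SE of a group mean = 13/√34 = 2.23. Half-widths of the 95% interval for the difference from placebo at 15 mg:

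- Direct comparison: 1.96 × 2.23 × √2 = 6.2 points.
- Linear model: Σ(d − 33.75)² = 3318.75, slope SE = 2.23/√3318.75 = 0.0387, half-width = 1.96 × 15 × 0.0387 = 1.1 points.
- Log-linear model: sum of squares of log(d + 1) about its mean = 11.22, slope SE = 2.23/√11.22 = 0.665, half-width = 1.96 × log(16) × 0.665 = 3.6 points.

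A linear fit with 9 points at 75 mg puts 15 mg at 9 × 15/75 = 1.8 ± 1.1 points. Under Emax with ED50 = 30 the true effect at 15 mg is 9 × (15/45)/(75/105) = 4.2 points, well outside.

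**3. Coverage.** For each true shape, 8,000 trials were simulated on the dose-group means. The five families were fitted by generalized least squares, the lowest AIC (least-squares criterion + 2p) was selected, and the selected model's interval was checked in trials with a significant MCP step. About 8,000 × 0.85 = 6,800 trials remain, so the Monte Carlo SE is near √(0.85 × 0.15/6,800) = 0.4 points.

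| Coverage, % | Linear | Log | Emax 20 | Emax 30 | Sigmoid | Quadratic |
|---|---|---|---|---|---|---|
| Mean, 15 mg | 85 | 86 | 85 | 83 | 80 | 82 |
| Mean, 30 mg | 87 | 86 | 84 | 83 | 84 | 81 |
| Mean, 45 mg | 92 | 92 | 91 | 92 | 88 | 83 |
| Mean, 75 mg | 94 | 93 | 93 | 93 | 93 | 92 |
| Difference, 15 mg | 82 | 75 | 64 | 53 | 79 | 58 |
| Difference, 30 mg | 88 | 78 | 72 | 73 | 86 | 71 |
| Difference, 45 mg | 93 | 93 | 91 | 93 | 95 | 85 |
| Difference, 75 mg | 97 | 97 | 97 | 97 | 96 | 96 |

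**4. Cause.** AIC chose linear or log-linear in about 76-89% of trials across the shapes. With the true family fixed in advance, and still conditioning on a significant MCP step, coverage at 15 and 45 mg is 95-98%. The loss therefore comes from selection, not from the conditioning.

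**5. Sensitivity.** With 30 per group, 15 mg coverage is 81-86% (mean) and 53-80% (difference). With SD 10 or 11 it is 77-86% and 54-83%; at 45 mg it is then 78-92% and 80-92%. Selecting only among models with a significant contrast gives nearly the same results.

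**6. With selection carried into the interval.** A parametric bootstrap repeating the AIC step (250 trials × 400 resamples per shape, Monte Carlo SE about 1.4 points) covers the mean 93-97% at 15 mg and 96-98% at 45 mg, and the difference 94-99% and 96-99%. The direct group means and differences cover 95-97% at every studied dose.

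**The case against.** The strongest reply is that little in the plan depends on this interval. The one formal claim is the MCP test, which is done before selection. The visible text has no target-dose estimate, minimum-effective-dose rule or go/no-go threshold that uses the curve CI. Valid estimates at 15, 45 and 75 mg are already planned from the MMRM. All of that stands, and it limits the consequence.

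Three further points also stand. Every candidate model includes E0, so the curve is more naturally the mean change than the difference from placebo, and the milder mean-curve figures come first. The CI method is inferred, and the simulated figures rest on the assumptions listed. And 30 mg is not a trial arm.

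What does not follow is that this is only missing detail. The MMRM estimates do not repair a curve interval printed as 95%, and they say nothing between studied doses. A reader shown both may prefer the narrower one.

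A reader might also infer that the plan would declare 15 mg effective almost regardless of that arm's data. In simulation the curve's interval for the difference at 15 mg does exclude zero in 91-100% of significant trials, against 9-50% for the direct comparison. But the documents make no such declaration from the curve, so this describes how the interval behaves, not a decision the plan takes.

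**Conclusion.** The stated 95% level is not delivered at the lower end of the curve. Rounded outward to cover repeat simulation runs, mean-curve coverage is about 80-86% at 15 mg, 80-88% at 30 mg, 83-93% at 45 mg and 92-94% at 75 mg. For the difference from placebo it is about 53-82%, 71-88%, 85-95% and 95-98%. These hold under the plan's own shapes, sample size, SD and effect, after a significant MCP test, with the assumptions in the working.

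It would be tempting to say that coverage is far below 95% at both the low and middle doses, or that the primary result is compromised. Neither is supported. At 45 mg the shortfall in mean-curve coverage is about 3-4 points under four of the six shapes, 7 under the sigmoid and 12 under the quadratic. At 75 mg coverage is close to nominal. The dose-response test and the MMRM means and differences remain valid at the studied doses. The change should be made, but it concerns only the fitted curve's interval.

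**What to change.** In SAP 7.3, state how the curve's 95% CI is obtained: draw parametric bootstrap samples of the MMRM LS means from their estimated covariance matrix, refit the five distinct models in each resample, repeat the AIC selection (or AIC weighting), and report percentile limits across the dose range. State the parameter bounds, and whether the curve is the mean change or the difference from placebo. Keep the MCP test, the candidate set and the AIC-best curve as planned. Overlay the MMRM estimates and their CIs at the studied doses.

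The LS means and covariance matrix are already planned outputs, so the cost is a paragraph and a short program. The price is visibly wider intervals: for the difference at 15 mg, mean width rises from about 4 to 6.5 points to about 9 to 10, still narrower than the direct comparison at 2 × 6.2 = 12.4 points. If the bootstrap is not adopted, the least that would serve is to name the CI method, label the interval as conditional on the selected model, and show the MMRM estimates beside it. That discloses the shortfall without correcting it.
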